**NCT05479123**

**Version Date: 06/02/2022**

**Protocol Title:** Assessing the Impact of Dosage Frequency of Propranolol on Sleep Patterns in Patients with Infantile Hemangiomas.

**Principal Investigator:** [name]

**Co-Investigators:** [name], [name], [name], [name], [name], [name]

**Sample Size:** 174

**Number of Sites:** Two study sites – Pediatric Plastic Surgery Clinic at the University of Texas Health Sciences Center at Houston and Dermatology Clinic at the University of Texas Health Sciences Center at Houston

**Study Duration:** Three years

**Subject Duration:** Up to age 18 months

**Version:** 1.4

**Most Recent Revision** 2/7/2022

---

**Research Question:**

In patients with infantile hemangioma, does three times a day (TID) dosing versus twice a day (BID) dosing of propranolol significantly improve subjective sleep scores?

**Background and Significance:**

Hemangiomas are the most common benign tumors of vascular endothelium in infants and children and are the most common tumors of childhood (Darrow et al., 2017). These vascular lesions often present as a colored patch of skin within the first days to months of life and occur focally, typically on the head and neck. Hemangiomas are unique because following their growth phase is a longer involution phase. The proliferative phase presents as a rapid, disordered proliferation of vasculature that is most evident during the first three to eight weeks of life. The subsequent involution is replaced by fibrous tissue over the next 4-6 years of life (Léauté-Labrèze et al., 2017). Despite being short lived, some hemangiomas present with complications of ulceration, permanent disfigurement, or physiologic restrictions (Tanner et al., 1998). Hemangiomas near the eye can lead to permanent strabismus and astigmatism, and tracheal hemangiomas can cause life threatening upper airway obstruction (Léauté-Labrèze et al., 2017).

A variety of treatment options exist for hemangiomas including oral and topical beta blockers, systemic corticosteroids, pulsed dye laser therapy, excisional surgery, and embolization. Propranolol was approved by the FDA in 2014 for the treatment of infantile hemangiomas and has since become the first line therapy. Propranolol's mechanism in the involution of hemangiomas is through induction of apoptosis and reduction of VEGF in epithelial cells. Propranolol as a treatment is able to both block growth and cause regression of infantile hemangiomas, leading to significant increases in the complete, or near complete, involution of the hemangioma compared to a placebo (Léauté-Labrèze et al., 2015). However, propranolol shows minimal effectiveness in treating hemangiomas after 18 months (Chang et al., 2017). While

rare, serious adverse effects exist for propranolol including hypotension, bradycardia, hyperkalemia, bronchospasm, and hypoglycemia (Léaute-Labrèze et al., 2016). For this reason, oral propranolol is not indicated for use in patients with existing cardiac or pulmonary disease. Additionally, sleep disturbances have been commonly reported as a side effect. Other beta blockers, such as atenolol and nadolol, have yielded promising data supporting their efficacy in the treatment of hemangiomas, with fewer side effects, but these trials have been small and limited (Bernabeu-Wittel et al., 2015). Regarding, superficial hemangiomas, topical beta blockers, like Timolol, have exhibited similar treatment outcomes as the oral form, and have resulted in fewer CNS side effects.

Prior to the FDA approval of propranolol for therapy of infantile hemangiomas, systemic corticosteroids were the primary therapy of choice for hemangiomas (Fost & Esterly, 1968). Although they have been largely replaced by propranolol, they serve as an alternative treatment modality for patients with contraindications to beta blockers. Despite the positive outcomes that can be seen using prednisone, the adverse effects of chronic steroid use may outweigh its efficacy in treating hemangiomas. Notably, the immunosuppression caused by corticosteroids increases the risk of infection in the patient and decreases the efficacy of some vaccines they are required to receive in their first two years of life (Boon et al., 1999).

In lieu of pharmacotherapy, pulsed dye lasers offer a noninvasive modality of treatment with great safety. However, they are primarily indicated for superficial hemangiomas as they only penetrate 1.2 mm (Stier et al., 2008). Excisional surgery can be used when medical treatment is unlikely to yield benefit or poses a greater risk, such as with residual scarring, noninvolved hemangiomas, or cosmetically concerning hemangiomas. The resultant post-surgical scar may be worse than the results of a spontaneous involution. Finally, embolization has been used as a last resort treatment, but some data suggests that the results may be temporary (Mcheik et al., 2005).

Overall, oral beta blockers have been the mainstay treatment for hemangiomas, but their association with sleep disturbances has continued to frustrate parents. Propranolol exhibits strong penetration into the blood brain barrier due to its lipophilicity. This penetration is likely exaggerated by the increased permeability of the blood brain barrier in infants (Vivas-Colmenares et al., 2015). Pediatric patients are thus at even higher risk of CNS side effects such as sleep disturbance and agitation. Parent reports of sleep impairments includes nightmares, insomnia, restlessness, increased waking, and overall sleep disturbance (Xerfan et al., 2020). While these sleep disturbances may be considered a minor side effect, the issue is cited as the most common reason for early discontinuation of propranolol (Ji et al., 2018).

The standard dosing regimen for oral propranolol for the treatment of infantile hemangiomas is twice a day (BID) dosage. In our multidisciplinary vascular anomalies clinic, parents of infants on propranolol for hemangiomas are queried at each visit regarding side effects. If a parent discusses concerns regarding sleep patterns, our standard protocol is to alter the regimen to three times a day (TID) dosage. While this seems to improve the sleep symptoms, there is no evidence to support this dosing schedule. The purpose of this study is therefore two-fold:

1. Assess the baseline sleep pattern disruption for patients starting oral propranolol at the standard BID dosing regimen compared to the control (timolol) group.
2. Determine if there is a significant improvement in the sleep patterns in infants taking oral propranolol on the TID dosing regimen versus the control (timolol) group.

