**Primary Outcome:**

1. Using the BISQ, number of sleep awakenings per night between the control (timolol) group and the BID propranolol group at 6 months on therapy.
2. . Using the BISQ, number of sleep awakenings per night between the control (timolol)group and the TID propranolol group at 6 months on therapy.

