**Sample Size:**

A sample size calculation was performed using best estimates in the literature provided by Theiler et al. (Theiler et al., 2021). Primary outcome was defined as number of awakenings per

night of sleep at 6 months of time on propranolol. In the Theiler et al study, patients on propranolol had 0.26 +/- 0.09 vs control patients of 0.21 +/- 0.1 awakenings per night. Utilizing a two-tailed analysis, we anticipate enrollment of 58 patients per treatment arm, giving our study 80% power with alpha 0.05. Given our number of annual patients (approximately 60 per year), we anticipate this study to be performed in 3 years. A concurrent Bayesian analysis will be performed.

We will analyze the data as two separate studies, each using the control (timolol) group as the reference. The BID propranolol group will be compared to the control group, as well as the TID group compared to control. This will allow us to see the effective change of sleep awakenings in each dosage group compared to control.

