### Prescription:

1. Control group: Patients with a small (<2cm) isolated infantile hemangioma are prescribed timolol 0.5% ophthalmic drops, a topical beta-blocker. Topical timolol has not demonstrated any concerns for sleep disturbances. Therefore, these patients will be enrolled as control patients in a non-randomized fashion.

Dosage for timolol 0.5% is 1 drop BID directly onto the hemangioma

2. Study groups: Patients with larger (>2cm) or multiple (>1) hemangiomas will be randomized to BID or TID dosage of propranolol. The prescription will be sent electronically to the pharmacy in the standard fashion for the practice. All patients will be initiated with the following schedule with medication administration to follow feeding:

Week 1: 0.5 mg/kg/day divided BID or TID

Week 2: 1 mg/kg/day divided BID or TID

Week 3: 2 mg/kg/day divided BID or TID. Patients will stay on this dosage until their 3 month follow up visit.

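### Purpose 2 seeks an improvement on TID propranolol over timolol, where the plan's own premises allow at best parity; the improvement belongs to TID versus BID

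*Combined protocol and SAP*

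**What the plan says.** Background and Significance closes with two purposes that share a comparator but look in opposite directions. Purpose 1 is to "Assess the baseline sleep pattern disruption for patients starting oral propranolol at the standard BID dosing regimen compared to the control (timolol) group". Purpose 2 is to "Determine if there is a significant improvement in the sleep patterns in infants taking oral propranolol on the TID dosing regimen versus the control (timolol)".

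The premises behind them are these:

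- **Timolol.** The Prescription section says "Topical timolol has not demonstrated any concerns for sleep disturbances", and gives this as the reason for using these infants as controls. They have small isolated lesions and are not randomised. Only BID versus TID is randomised.
- **Propranolol.** Background and Significance says of its effect on the brain: "Pediatric patients are thus at even higher risk of CNS side effects such as sleep disturbance and agitation".
- **Where TID is thought to help.** The clinic moves infants from BID to TID when parents report sleep problems: "While this seems to improve the sleep symptoms, there is no evidence to support this dosing schedule".
- **Sizing.** Sample Size relies on a cohort in which "patients on propranolol had 0.26 +/- 0.09 vs control patients of 0.21 +/- 0.1 awakenings per night".

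Primary outcome 2 is the "number of sleep awakenings per night between the control (timolol)group and the TID propranolol group at 6 months on therapy". It states no direction and no margin. Sample Size specifies two-tailed analysis, with BID and TID each compared with timolol as separate studies.

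The Research Question and PICO ask about TID versus BID. The Hypothesis is that TID's gap from control is smaller than BID's.

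**The concern.** Purpose 2 asks for a gain over a comparator that is assumed not to disturb sleep. If TID removed every trace of the propranolol effect, TID infants would be expected to sleep like timolol infants, not better. Read literally, the purpose would then fail although the regimen had worked completely.

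The practical risk lies at the reporting stage. Of the two planned tests, the TID result most compatible with success is a non-significant difference from timolol. No margin or other criterion says how large a remaining excess that result may conceal. At this sample size it is also a common result when TID still disturbs sleep, and it can sit beside a significant BID result when the two regimens do not differ.

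**Working it through.** **Inputs** (Sample Size section): propranolol mean 0.26, SD 0.09; control mean 0.21, SD 0.10; difference 0.05 in the direction of harm; two-sided alpha 0.05; 80% power; 58 per arm.

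**1. The plan's own figure.** n = (1.96 + 0.842)² × (0.09² + 0.10²) / 0.05² = 7.85 × 0.0181 / 0.0025 = 56.8, so 57. The t-test version gives 57.8, so 58. The stated size is reproduced. Power at 58 per arm is 80.8% (normal) or 80.1% (t).

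**2. Precision of TID minus timolol.** SE = √(0.09²/58 + 0.10²/58) = 0.0177. The 95% half-width is 1.96 × 0.0177 = 0.035, so an observed difference of about 0.035 is needed for significance.

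**3. What the TID-timolol test can show.** Let δ be the true TID excess over timolol. Then P(significant improvement) = Φ(−1.96 − δ/SE) and P(significantly worse) = 1 − Φ(1.96 − δ/SE). The documents give no TID effect, so the three values of δ below are assumptions running from no excess to the full excess.

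| True TID mean | δ | δ/SE | Significant improvement | Significantly worse | Non-significant |
|---|---|---|---|---|---|
| 0.21 (whole excess removed) | 0 | 0 | 2.5% | 2.5% | 95% |
| 0.235 (half remains) | 0.025 | 1.42 | 0.04% | 29.3% | 70.7% |
| 0.26 (all remains) | 0.05 | 2.83 | below 0.001% | 80.8% | 19.2% |

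The t-test gives about 71% and 20% for the last two non-significant figures. The 2.5% in the first row is only the lower-tail type I error, so it does not depend on the SD.

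**4. Reading the two tests side by side.** One million simulated trials used normal arm means and the shared timolol arm. With BID and TID both at 0.26, BID was significantly worse and TID non-significant in 10.4% of trials. With both at 0.235 the figure was 13.4%. In about 86% of those trials a direct TID-BID test was not significant.

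**5. Precision of the randomised contrast.** For TID minus BID with SD 0.09 in both arms, SE = 0.09 × √(2/58) = 0.0167 and the half-width is 1.96 × 0.0167 = 0.033. Power at 58 per arm is 84.9% if TID removes the whole 0.05 and 32.1% if it removes half. With SD 0.10 these become 76.8% and 27.0%.

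**The case against.** The strongest reply is that only one sentence in the Background is directional. Primary outcome 2 names no direction and the analysis is two-tailed, so the endpoint itself is not aimed the wrong way. That stands, and it confines the direction fault to the wording of purpose 2.

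A reader might go further in three ways that the documents do not support:

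- **That the premises rule out a TID advantage over timolol.** They make it implausible. The timolol arm is non-randomised and limited to small isolated lesions, so confounding could move the difference either way.
- **That a non-significant result is the only one that could favour TID.** Under the Hypothesis, TID could be significantly worse than timolol and still be favoured if its excess were smaller than BID's. No test of that contrast is set out, and the concurrent Bayesian analysis is mentioned without estimand, prior or decision rule.
- **That the plan will count a null result as success.** No section says so. The plan simply contains nothing to prevent that reading.

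It can also be said that this is one symptom of the missing TID-BID comparison. Largely so, since restating purpose 2 against BID removes the direction problem. But adding that comparison would not by itself settle how a non-significant TID-timolol result is to be read.

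One might instead keep timolol as the benchmark and claim a benefit if the upper 95% limit falls below 0.05. This is not a sound rescue. The 0.05 comes from an outside cohort and would be applied to a non-randomised contrast. The rule would be met about 80% of the time whenever TID matches timolol, even if BID matched it too, so it cannot show an advantage over BID. With half the excess remaining it is met only Φ((0.05 − 0.025)/0.0177 − 1.96), about 29% of the time.

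**Conclusion.** The point holds as a fault in purpose 2 and in what the TID-timolol test can support. It does not hold as a fault in the direction of the primary outcome. If TID removes the whole excess, the stated improvement over timolol is found in about 2.5% of trials. A non-significant TID-timolol result arises about 71% of the time with half the excess left and 19-20% with all of it. The contrasting pattern of BID significant and TID not arises in about 10% of trials when both carry the same 0.05 excess.

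These figures rest on the quoted means and SDs, on normal arm means, and on all 58 per arm being evaluable at 6 months. The total of 174 is 3 × 58, with no dropout allowance stated. The SDs deserve a check. If each infant's answer is a whole number (an assumption), a mean of 0.21 forces an SD of at least √(0.21 × 0.79) = 0.41, and every interval would be much wider. The 2.5% and the argument about direction would not change.

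**What to change.** 1. **Background and Significance, purpose 2.** Restate the improvement as TID versus BID, in line with the Research Question, PICO and Hypothesis. Report the randomised difference in awakenings per night at 6 months with its 95% CI. The expected half-width is about 0.033 at 58 per arm if the SD is 0.09.
2. **Primary Outcome, item 2.** Reword as an estimate of the excess in awakenings per night on TID propranolol over timolol at 6 months, with its 95% CI (half-width about 0.035). Label it a non-randomised reference comparison.
3. **Sample Size, analysis paragraph.** State that a non-significant TID-timolol difference will not be read as absence of sleep disturbance. Also state that a significant BID result beside a non-significant TID result will not be read as a difference between the regimens. Add no upper-limit-below-0.05 claim.

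The cost is wording only, with no extra patients or data. The downside is that a non-significant TID-timolol result can no longer be presented by itself as favouring TID. The sponsor should also accept that, at 58 per arm, the TID-BID interval will often be inconclusive if TID removes only part of the excess.

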## PICO

P: In patients with infantile hemangiomas  
I: does TID dosing of oral propranolol versus  
C: standard BID dosing of oral propranolol  
O: result in a significant improvement in subjective sleep scores

**Hypothesis:**

We anticipate that patients receiving the TID dosing regimen of oral propranolol will demonstrate fewer sleep awakenings compared to the control group than the BID dosing regimen compared to the control.

**Study Setting:**

This is a prospective study involving patients who present to the Vascular Anomalies Clinic at the University of Texas Health Sciences Center at Houston and the Dermatology Clinic at the University of Texas Health Sciences Center at Houston. This patient population consists of patients with the diagnosis of infantile hemangioma(s).

**Study Population:**

Inclusion Criteria:

1. Patients with clinically diagnosed hemangiomas.
2. Age <18 months
3. English or Spanish speaking only

Exclusion Criteria:

1. Parents who do not consent to the study.
2. Significant cardiac or pulmonary disease who are unable to tolerate oral propranolol
3. Age >18 months
4. Non-English or Spanish speaking parents.

**Study Design:**

Prospective, single center, randomized controlled trial – parallel groups

**Primary Outcome:**

1. Using the BISQ, number of sleep awakenings per night between the control (timolol) group and the BID propranolol group at 6 months on therapy.
2. . Using the BISQ, number of sleep awakenings per night between the control (timolol)group and the TID propranolol group at 6 months on therapy.

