### Sleep Survey:

In this study, we propose to use the Brief Infant Sleep Questionnaire (BISQ) to record and quantify caregiver reports of infant sleep. The BISQ has been validated as a multi-dimensional survey for evaluating infant sleep due to its reliability and high specificity of sleep parameters (Sadeh, 2004; Del-Ponte et al., 2020). Parents will be offered this study at each of the clinic visits (every 3 months) from the date of initial prescription until termination of the medication (18 months of age). Patients in all three groups (Timolol, BID Propranolol, and TID Propranolol) will be given this survey.

Follow up: Once a prescription is initiated, all patients with infantile hemangiomas stay on the medication until 18 months of age. Patients are seen every three months, either in person or virtual visits. During that visit, a recent weight is used to adjust their dosage of the oral propranolol to the new appropriate level. Each of these visits will be an opportunity for the sleep survey to be given.

Study Termination: After 18 months of age, all patients are removed from medication (timolol and propranolol). After this visit and final sleep assessment, all patients will be removed from the study.

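### An infant who stops before six months has no primary outcome value, and no analysis is stated for stoppers or BID-to-TID switchers, so the primary comparison can select on sleep itself

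*Combined protocol and SAP*

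**What the plan says.** The Primary Outcome section defines two comparisons of awakenings per night: the control group "and the BID propranolol group at 6 months on therapy", and the control group against the "TID propranolol group at 6 months on therapy". The Sample Size section uses the same clock, counting awakenings per "night of sleep at 6 months of time on propranolol". In both places time is measured by exposure to the drug, not from randomisation or first prescription.

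Under Sleep Survey, the BISQ is offered at the three-monthly visits "from the date of initial prescription until termination of the medication (18 months of age"). The Follow up paragraph there states that "all patients with infantile hemangiomas stay on the medication until 18 months of age". The Study Termination paragraph places exit from the study after 18 months of age: "After this visit and final sleep assessment, all patients will be removed from the study".

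The Background and Significance section says of sleep disturbance that "the issue is cited as the most common reason for early discontinuation of propranolol". It adds that when a parent raises sleep concerns, "our standard protocol is to alter the regimen to three times a day (TID) dosage".

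The plan contains no as-randomised statement, no rule for analysing infants who stop or change frequency, and no missing-data method.

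**The concern.** The outcome is sleep, and the Background gives sleep as the usual reason for stopping the drug. If the primary value exists only for infants who reach six months on treatment, the poorest sleepers may be missing from the propranolol groups. Little matching loss would be expected on timolol, because the Prescription section says it has raised no sleep concern. The excess of propranolol over control would then be understated.

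BID and TID are each compared separately with timolol, so unequal loss also matters. The regimen that loses more poor sleepers looks better. Randomisation between BID and TID does not protect against this, because the selection happens afterwards.

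Switching raises a related problem. A BID infant moved to TID for poor sleep stays on therapy and can be surveyed, but the plan does not say in which group that infant counts. If infants were grouped by the frequency received, poor sleepers would move from BID into TID.

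**Working it through.** **The plan's own figure.** Inputs from the Sample Size section: 0.26 (SD 0.09) on propranolol, 0.21 (SD 0.10) on control, two-sided alpha 0.05, 80% power, 58 per arm.
- Difference = 0.26 − 0.21 = 0.05.
- Pooled SD = √((0.09² + 0.10²)/2) = 0.0951.
- The t-test requirement is 57.8, so 58 per arm. Power at 58 is 80.1%.

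The stated number is reproduced. It contains no allowance for loss.

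**Effect of stopping, if 0.26 is the mean of all starters.** The documents give no stopping rate, so the rates are assumptions. Let a fraction p of a propranolol arm stop, and let stoppers average k SDs (k × 0.09) above the arm mean. The mean of those remaining is (0.26 − p(0.26 + 0.09k))/(1 − p), so

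observed excess = 0.05 − 0.09·k·p/(1 − p).

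Power is from a pooled-variance t-test of 58(1 − p) propranolol infants against 58 controls, with SDs held at 0.09 and 0.10.

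| p | k | Infants left | Observed excess | Power |
|---|---|---|---|---|
| 5% | 0.5 | 55.1 | 0.05 − 0.00225/0.95 = 0.048 | 75% |
| 10% | 1 | 52.2 | 0.05 − 0.009/0.90 = 0.040 | 59% |
| 20% | 1 | 46.4 | 0.05 − 0.018/0.80 = 0.028 | 30% |

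**Effect of stopping, if 0.26 is already an on-drug mean.** The excess among those remaining stays at 0.05 and only numbers are lost. Power is 79%, 78% and 75% at 5%, 10% and 20% stopping. Stopping unrelated to sleep gives the same figures. The gap between these figures and the table is therefore due to selection, which a larger sample would not remove.

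**BID against TID.** Suppose the two regimens have the same true effect. If 10% of one arm stop at 1 SD and 5% of the other at 0.5 SD, the excesses over control read 0.040 and 0.048. That is a gap of about 0.008 with no true difference, in favour of the arm that lost more. Exchanging the arms reverses the sign.

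**What surveying everyone would estimate.** Take the 10%, 1 SD case, where the 90% still on drug average 0.25 and the stoppers averaged 0.26 + 0.09 = 0.35 on drug.
- Stoppers return to the control mean: 0.9 × 0.25 + 0.1 × 0.21 = 0.246, an excess of 0.036 with power 52%.
- Stoppers lose only the 0.05 drug effect (0.35 − 0.05 = 0.30): 0.9 × 0.25 + 0.1 × 0.30 = 0.255, an excess of 0.045 with power 71%.

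Neither case restores 0.050.

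**The case against.** A reader might infer that surveys cease when an infant stops, so that stoppers leave the study by rule. The documents do not support this. Sleep Survey ties the end of medication to a fixed age, makes every three-monthly visit a survey opportunity, and removes patients only after 18 months of age. It is silent on an early stop. The point rests instead on the outcome definition, which gives an early stopper no primary value even if that infant is surveyed.

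A reader might also see a flat contradiction between the Background and the statement that all infants stay on drug. The Background reports a cited source on stopping in general, while Follow up describes this clinic. The clinic's stated response to sleep complaints is a change of frequency, and Safety Measures reports no adverse effects in over 1000 patients. Stopping may therefore be uncommon here. Even so, Safety Measures lists events that may lead to stopping, and switching is equally unaddressed in the analysis.

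The larger power losses depend on reading 0.26 as the mean of all starters. The Sample Size section attributes it to patients on propranolol, which may already be an on-drug figure. The documents do not settle which reading is right.

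An on-treatment effect can be a legitimate target, and surveying off-drug infants does not recover the pure on-drug excess. Both objections stand. However, the plan neither chooses nor justifies an on-treatment target, and sets no as-randomised analysis beside it.

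**Conclusion.** The point holds in a limited form. By its own definition, the primary outcome excludes infants who stop before six months, and the plan assigns no analysis to stoppers or switchers. Because the Background links both events to sleep, the primary analysis can select on the outcome after randomisation and distort the contrast that the research question asks about.

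The documents do not give the size. Under the assumed rates, power lies between 75% and 30% if 0.26 describes all starters, and between 79% and 75% if it is an on-drug mean. These figures are illustrations, not estimates of what will happen. It would also go too far to say that the bias hides a TID benefit. That requires BID to lose more poor sleepers than TID, and the documents do not show which way any imbalance would run.

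The sample size calculation is not at fault. This should be fixed, and cheaply, but nothing here shows that the trial is invalid without the change.

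**What to change.** - Define the primary time point as 6 months after first prescription.
- Collect the BISQ then from every enrolled family, whether or not the infant is still on the drug or the assigned frequency.
- Analyse BID and TID infants as randomised. The timolol group is enrolled without randomisation and stays as enrolled.
- Record the date and reason for any stop or change of frequency.
- Keep the on-therapy analysis as supportive.
- Reconcile Background and Significance, Primary Outcome, Sample Size and Sleep Survey on how long infants are treated, what happens after an early stop, and which clock defines six months. The exit rule at 18 months of age needs the same check, because an infant first prescribed after 12 months of age (18 − 6) passes it before the six-month survey.

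The cost is a wording change and one extra BISQ for families who have stopped. Virtual visits are already allowed. The main downside is an estimate that mixes on-drug, off-drug and switched infants, so it may be smaller than the pure on-drug excess. The gain is a BID and TID comparison that is not selected on sleep. The sample size and all dosing and clinical rules are left as they are. Six-month surveys that are not collected cannot be recovered later, so the change is best made before infants reach that point.
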